10.8.2 Data Sharing Plan

Intellectual property and data generated under this project will be administered in accordance with NIH policies, including the NIH Data Sharing Policy and Implementation Guidance of March 5, 2003. Materials generated under the project will be disseminated in accordance with KEMRI, University of Washington, University of Colorado, and NIH policies. Depending on such policies, materials may be transferred to others under the terms of a material transfer agreement. Access to databases and associated software tools generated under the project will be available for educational, research, and non-profit purposes. Such access will be provided using web-based applications, as appropriate. Publication of data shall occur during the project, if appropriate, or at the end of the project, consistent with normal scientific practices. Research data that documents, supports, and validates research findings will be made available after the main findings from the final research data set have been accepted for publication. Such research data will be modified to prevent the disclosure of personal identifiers to remain in compliance with the Protection of Human Subjects guidelines.

10.8.3 Collaborative research

The proposed project is a collaborative effort between NIH/NAIDS, UW, UC, and KEMRI. The aforementioned institutions will jointly share ownership of the data. Authorship on publications, conference presentations, abstracts and other materials generated from this program will reflect contribution to design, execution and analysis of the program data.

10.8.4 Dissemination plan

Dissemination of study results will follow principles of good participatory practice. Study results will be disseminated through presentations to stakeholders and policymakers and published in conference abstracts and peer-reviewed journals.

We will disseminate the results from this research as broadly as possible. Of note, drafts of publications will be shared with the NIH program office and medical officer prior to submission. First, we will publish our results in Open Access journals, if appropriate. Second, we will post author PDFs of our manuscripts on our respective websites in accordance with the copyright rules of the journals.

10.8.5 Presentations

We expect that all the research personnel will attend national conferences periodically and present the results from this research to the scientific community. Because of the multidisciplinary nature of the work, different group members will present at various conferences, such as the Conference on Retrovirus and Opportunistic Infections, International AIDS Society, and Kenya-based conferences, which focus on the appropriate aspects of our research.

The study team for this award is committed to public dissemination of results of clinical trial, to trial participants, local stakeholders in Kenya, the global scientific community, and US, Kenyan, and global policymakers. Dissemination of study results will follow principles of good participatory practice. The clinical trial will be registered with Clinicaltrials.gov prior to initiation and results will be updated there in a timely fashion. Results will be published in conference abstracts and peer-reviewed journals. Study results will be disseminated through presentations to local stakeholders and policymakers in Kenya, including the Ministry of Health.

10.9 Intellectual property consideration

There is no commercial value for this work. The proposed project is a collaborative effort between NIH/NAID, UW, UC, and KEMRI. All data collected as part of this implementation program will be made available without cost with written request and agreement to the data sharing agreement after completion of primary analyses. The data sharing agreement will ensure commitments to:

- Using the data only for program evaluation purposes and without attempting to identify patients
- Securing the data using appropriate computer technology
- Destroying or returning the data after analyses are completed
- Restrictions on redistribution of the data to third parties
- Proper acknowledgement of the data resource.

11 TIMELINES

We have planned for an efficient time-sensitive four-year project, given the timely nature of the question (Table 7).

Table 7		Project Years	Y1				Y2				Y3			
AIM	MILESTONE	Quarter	Q1	Q2	Q3	Q4	Q1	Q2	Q3	Q4	Q1	Q2	Q3	Q4
Funding	Funding Announced													
Protocol Planning	Protocol Development													
	IRB Submission, SOP development													
Protocol Execution	Enrollment, follow up in DOT study, pharmacologic sample collection													
	Regulatory application from MOH and IRB to ship samples													
	Ship DOT pharmacologic samples													
	Test DOT study samples													
	Statistical analyses and compilation of full spectrum of results													
Dissemination	Writing and results dissemination													

12 EXPECTED APPLICATION OF RESULTS

The study will be the first to define TDF-PrEP adherence-concentration thresholds in Africa cisgender women, a population facing significant burden of incident HIV infection. Knowledge gained from the proposed study will include key concentration of PrEP medications associated with HIV protection and the required adherence to achieve those concentrations for cisgender women, and optimal dosing for PrEP in at-risk pregnant cisgender women. In addition, data from this work will help to estimate the quantitative concentrations of PrEP medication associated with protection against HIV in cisgender women and adherence required to generate those concentrations. The results of this work will have immediate implications for the global PrEP programs among cisgender women.

13 STUDY LIMITATIONS

The study team recognizes potential limitation of the proposed work which may include: 1) Part of preliminary data are not from DOT studies and that observed effects might be due to correlation between MEMS and blood levels and not related to pharmacologic differences between US male and African cisgender women blood levels. However, we take confidence in fact that our pregnancy data from the same population have been replicated by the IMPAACT 2009 study; 2) Intensive sampling for individual PK parameters is not planned as that is well defined. DBS exhibits a long half-life and is not suited for intensive PK. Nevertheless, plasma steady-state levels while it does not pinpoint the mechanism for PK differences, it will indicate whether or not recent PK exposure differs and by how much. Furthermore, population PK models will be developed to determine individual-level PK in plasma.

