Only cisgender women with an active smart phone will be enrolled and will be supported with weekly data/internet bundles consistent with the local IRB. The remote DOT via video streaming is intended to increase compliance as well as minimize participant burden, especially pregnant cisgender women.

Home visits: We will conduct complimentary home visits for patients unable to attend their scheduled clinic visits or procedure to promote compliance to study procedures. During home visits, study staff may conduct study procedures e.g., observing of dosing taking or collection of study samples (blood, urine, hair) where applicable. Any offsite collection of study sample will follow the same safety standards followed at the clinic. For this pharmacological study, only cisgender women who consent for home visits will be enrolled.

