4.8 HIV Seroconversion

Frequent testing for HIV acquisition during the study period will allow prompt cessation of study drug in an HIV-infected participant, minimizing the risk that resistant virus will emerge. Therefore, HIV testing will be performed at all monthly study visits. HIV rapid testing and specimen collection should be completed prior to administration of study medication. Participants who have any reactive or positive HIV test result after initiating PrEP will be instructed to discontinue study drug immediately and will have further testing to clarify their HIV infection status, as described in Section 5.3. Any enrolled participant who is confirmed

to have acquired HIV infection during the study will permanently discontinue study product and will be transitioned to a local HIV care clinic for appropriate follow-up and clinical management. Procedures for participants who acquire HIV infection are described in Section 5.3.

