asking the participant to show that their mouth is empty. Flexible clinic scheduling will be available to promote high rates of follow-up and compliance and minimize participant's burden. Where dosing cannot be witnessed in person, dosing will be witnessed by video communication via WhatsApp, Zoom, FaceTime, Skype, or other video-streaming device that is agreed upon by the participant and study personnel will be used. Only cisgender women with an active smart phone will be enrolled in this pharmacological study to permit offsite observation of dose taking for the required DOT PrEP. Participants will be supported with commensurate data/internet bundles. A one-month supply of back-up medication will be provided to participants at study enrollment to be used if participant is unable to complete visit at the clinic. All these doses taken offsite will still be directly observed by study staff by live video streaming and participants will be asked to open their mouth afterwards to confirm swallowing. Dosing may occur at variable times within the assigned dosing day. All doses will be taken without regard to food, but meal information will be collected with each dosing event.

Study personnel will use a dosing log to document directly observed doses. Participants will be given a detailed calendar that shows scheduled dosing days. This schedule will also be reinforced when study personnel interact with participants.

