5.2.3.1 Specimen collection

All pharmacological samples must be collected as per protocol-specified schedule. Each protocol-specified pharmacological sampling visit will have a window of up to 3 days (up to week for hair) for sample collection. The following pharmacological samples will be collected as follows:

Blood collection

A blood sample will be obtained at protocol specified visits to process plasma, whole blood, DBS, and PBMCs. On a given study day blood collection, up to 21-mL draw with no planned timing relationship with dosing. The blood will be collected from an arm vein by trained clinic staff according to study site policies and procedures.

The schedule of protocol visits and procedures are outlined in Table 5.

Table 5: Schedule of protocol visit schedule and procedures.

	Screening	Entry	DOT PrEP Period (weeks)										Post DOT Period	
Timeline (weeks)			W1		W2	W3	W4	W5	W6	W7	W8	W9	W10-16	
			Day 4	Day 7										
Clinic Visits #		1	2	3	4	5	6	7	8	9	10	11	12	
Procedure														
Informed consent	x													
Medical, sexual, contraception, antenatal history review, vaccine history	x	x	x	x	x	x	x	x	x	x	x			
Physical and obstetric exam ^a	x													
Fetal ultrasound for pregnant women*	x													
Dispense back up PrEP medication ^e		x												
Issue medical calendar		x												
AE assessment		x	x	x	x	x	x	x	x	x	x			
Safety Labs ^{a,c}	x	[x]									x			
Urine β HCG ^a	x	[x]					x				x			
HBS Ag	x													
HIV-1 rapid test ^a	x	[x]					x				x			
Hair collection							x				x		x	
hDNA		x		x										
Study Bloodwork ^d (WB, plasma, DBS, PBMC)**		x	x	x	x	x	x	x	x	x	x	x	x	
Vaginal tissue- non-pregnant only ^f			x	x			x				x			
Vaginal swab		x	x	x			x				x			
DBS by fingerstick			x	x			x				x			
Study Urine ^d		x	x	x	x	x	x	x	x	x	x	x	x	
Concomitant Medication Review	x	x	x	x	x	x	x	x	x	x	x			
STI testing		x												
DOT ^b		x	x	x	x	x	x	x	x	x	x			

[x] Indicated if screening occurred more 30 days before planned enrollment. The screen and entry visits must be ≤ 30 days apart.

*If women has no record of fetal ultrasound for the current pregnancy, ultrasound must be conducted before enrollment.

**Blood works for pregnancy women only at week 0, 1, 2, 4, 6, 8, 9

a. Safety labs or vitals can be performed as needed at any time

b. DOT performed if applicable per randomization schedule

- c. Protocol-specified safety labs include: CBC, HBAg, Creatinine clearance, in addition to monthly HIV testing and urine pregnancy tests.

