7.3.2 Secondary outcomes

1. Examine models to predict non-daily adherence based on TFV/FTC and TFV-DP in DBS.

We assume the modeling approaches of Aim-1. We will first consider a saturated model allowing a separate mean for each dose/adherence group. The results will then be compared to a reduced model with a class variable indicating non-daily dosing groups” or 100% dosing (that is, the effect of “non-daily dosing” adherence does not differ by dose groups). Drug concentration predictors of “non-daily dosing” will focus on TFV-DP in relationship to other drug moieties such as FTC-TP and FTC and TFV. For instance, the ratio of TFV-DP to FTC-TP may be used as a predictor of “2” versus “4 dosing per week. A proportional odds logistic approach which allows for an ordinal outcome and extensions which control for correlations between repeated measurements on a subject will be utilized in SAS or R statistical software. In addition, we will employ PK models (see Aim-1) to simulate TFV-DP to FTC-TP ratios for other dose regimens and estimate cut points for predicting non-daily dosing patterns.

2. To quantify the effect of pregnancy on the benchmark concentrations of TFV, TFV-DP, FTC, and FTC-TP in pregnant cisgender women using daily DOT FTC-TDF PrEP.

Using modeling approaches, we will compare the benchmark concentrations of TFV, FTC, TFV-DP, and FTC-TP between pregnant cisgender women using daily DOT FTC-TDF PrEP. Analyses will be stratified by age and pregnancy gestation.

3. Examine relationships among drug concentrations in plasma, RBC, DBS, and PBMC.

We will use mixed and non-linear mixed effects models to determine if concentrations in various matrices are related.

4. Evaluate the influence of demographics, biological) on drug concentrations.

Kruskal-Wallis parametric test will be used to compare demographics and key study variables (e.g., age, pregnancy, mean corpuscular volume and HCT, contraception use, study arm, BMI, eGFR). Secondary analyses are considered hypothesis generating and will not correct for multiple comparisons.

5. Compare drug concentrations in DBS from fingerstick versus transferring blood from blood tubes.

Since these are paired DBS samples, we will compute the ratio of TFV-DP in the two samples and a mixed model on the natural log of the ratio will be utilized to determine if CI is within 0.8 and 1.25, indicating equivalence. Bland-Altman analyses will also be evaluated.

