9 LABORATORY SPECIMENS AND BIOHAZARD CONTAINMENT

9.1 Laboratory evaluations and specimen collections

The following safety and monitoring laboratories will be collected at regular intervals during the study as described above: complete hematology panels, pregnancy tests (urine), and HIV (rapid or regular), serum creatinine, (estimated creatinine clearance), and HBV surface Ag test. The HIV and HBV tests will be used to screen HIV-negative volunteers for inclusion in the study. The tests are provided according to established laboratory procedures at site. These clinical laboratories/sites conform to CAP and/or CLIA-regulations, and the results will be posted to the medical record as positive or negative.

All pharmacological samples will be collected, processed, and stored according to standard operating procedures developed by the Colorado Antiviral Pharmacology Laboratory. On each pharmacological sample visit day, samples will be collected without regard to the dosing time within each day (i.e., sampling at convenience times rather than troughs). The only exception will be at the entry visit to be obtained at pre-dose. We will take a comprehensive approach to establish benchmark adherence-concentration thresholds for cisgender women and pregnant cisgender women using daily DOT TDF/FTC

PrEP by collecting samples for pharmacological measurements in multiple biologic matrices: plasma, whole blood, DBS, PBMCs, and vaginal tissue (non-pregnant cisgender women only) and archiving urine and hair samples. All cisgender women (non-pregnant and pregnant) will contribute to this comprehensive assessment during the up to 16 weeks of follow up (8 weeks of DOT PrEP and up to 8 weeks post DOT PrEP for post drug kinetics). Within each group, we will collect pharmacologic samples (plasma, whole blood, DBS, PBMCs) to measure the respective concentrations of TDF/FTC moieties at day 4 and weekly up to 8 weeks with daily DOT PrEP dosing and at week 9 and weeks 10-16 post DOT PrEP period, and in nonpregnant cisgender women, vaginal tissue at day 4, week 1, 2, 4, and 8.

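### The plasma TFV and FTC comparison between pregnant and non-pregnant women ignores time since the last dose, so section 13's promise to say by how much exposure differs is not supported as written

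*Combined protocol and SAP*

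**What the plan says.** Section 13 accepts that intensive sampling is not planned and says of plasma steady-state levels that "it will indicate whether or not recent PK exposure differs and by how much". The next sentence adds that "population PK models will be developed to determine individual-level PK in plasma".

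On timing, 5.2.3.1 describes an "up to 21-mL draw with no planned timing relationship with dosing", and 9.1 says that "samples will be collected without regard to the dosing time within each day", with the entry sample as the only pre-dose exception. Section 5.2.1 adds: "Dosing may occur at variable times within the assigned dosing day". It provides for a dosing log, but neither that section nor any other says that the clock time of the dose or of the draw is recorded. Section 4.8, on HIV testing at the monthly visits, says: "HIV rapid testing and specimen collection should be completed prior to administration of study medication".

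Section 7.3.1 argues that time after dose can be ignored, and gives the 17-day half-life of TFV-DP as the reason. Section 7.3.2(2) compares TFV, FTC, TFV-DP and FTC-TP by pregnancy. Its only stated adjustment is "Analyses will be stratified by age and pregnancy gestation". The sentence does not name the comparison group; 2.5.2 implies the non-pregnant daily arm, to which the pregnant women are matched on age.

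**The concern.** Convenience sampling is justified for a moiety that barely moves within a day. Section 13 then relies on plasma as a marker of recent exposure. An analyte that reflects recent dosing depends on when the last tablet was taken, and the reason given for TFV-DP does not carry over to it.

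Two consequences follow. If draw times scatter in the same way in both cohorts, the comparison loses precision. If they differ systematically, the pregnant to non-pregnant ratio is biased: it can show a difference where there is none, or mask part of a true fall. The cohorts are not randomised against each other, so nothing in the design balances timing. One possible route to imbalance is remote video dosing, which 3.6 says is "intended to increase compliance as well as minimize participant burden, especially pregnant cisgender women".

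**Working it through.** **Inputs from the documents.** Half-life of TFV-DP in DBS: 17 days (5.2.1). CV 25.2%, for DBS TFV-DP in US men (7.4). Group size 18, with 10% non-completion allowed for (7.4): 18 × 0.9 = 16.2, so 16 v 16. Expected pregnancy effect (1.2.3): 30% to 40% lower for DBS TFV-DP, pregnant v postpartum, in an earlier directly observed study; 45% to 58% lower for TFV and TFV-DP in the investigators' earlier data. On-treatment blood in pregnant women: weeks 1, 2, 4, 6 and 8 (Table 5 footnote), so five visits.

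**Assumed.** The documents give no plasma half-life h and no plasma CV. I take h = 12 to 24 h with single-exponential decline, and borrow the 25.2% CV.

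**1. The plan's own figure.** Share of steady state at week 8 = 1 − 2^(−56/17) = 89.8%, which reproduces its approximately 90%. With the same half-life, DBS TFV-DP falls 1 − 2^(−1/17) = 4.0% in 24 h. Ignoring time after dose is reasonable there.

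**2. Plasma over one daily interval.** Fall = 1 − 2^(−24/h): 75% at h = 12, 50% at h = 24.

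**3. Haphazard timing, alike in both cohorts.**
- Between-woman log-SD = √ln(1 + 0.252²) = 0.248.
- Log-SD from draw times uniform over 24 h = (ln 2/h) × 24/√12 = 0.400 (h = 12) or 0.200 (h = 24).
- One draw per woman: variance multiplier = (0.248² + 0.400²)/0.248² = 3.60, or with 0.200², 1.65.
- Mean of five independently timed visits: (0.248² + 0.400²/5)/0.248² = 1.52, or 1.13.
- Factor either side of the ratio for a 90% CI = exp(1.697 × SD × √(2/16)). With no timing scatter it is 1.16; with one draw, 1.21 (h = 24) to 1.33 (h = 12); with five visits, 1.17 to 1.20.

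**4. Systematic gap of d hours in mean time since dose.** Spurious difference = 1 − 2^(−d/h).

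| Gap | h = 12 | h = 24 |
|---|---|---|
| 4 h | 21% | 11% |
| 8 h | 37% | 21% |

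Masking works the same way. If pregnant women were drawn 4 h sooner after dosing, a true 30% fall would read as 0.70 × 2^(4/12) = 0.88 or 0.70 × 2^(4/24) = 0.79, that is 12% or 21% lower.

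**5. Gap needed to mimic the expected effect r.** d = h × log2(1/(1 − r)).

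| Effect | h = 12 | h = 24 |
|---|---|---|
| 30% | 6.2 h | 12.3 h |
| 45% | 10.3 h | 20.7 h |
| 58% | 15.0 h | 30.0 h |

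**The case against.** The strongest reply is that the plan already promises population PK models for plasma. Such a model ordinarily uses time since dose and could deal with the problem. That narrows the point without removing it: the models are not described, pregnancy is not named as a covariate, 7.3.2(2) does not refer to them, and the clock times they would need are not stated to be recorded.

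A systematic gap is also not shown. In-person observation is the rule in both cohorts and video the fallback (4.3, 5.2.1). Table 5 lists observed dosing at every on-treatment sampling visit. Section 3.6 does not say that pregnant women will dose at home on sampling days. This stands, and the 4 h and 8 h figures are illustrations only. Repeat visits also reduce the noise, as step 3 shows, though averaging would not remove a systematic gap.

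The sentence in 4.8 sits under HIV seroconversion and may mean HIV specimens only. If it does cover pharmacology blood, samples at the monthly visits would precede that day's clinic dose in both cohorts, which would weaken the bias argument. It would also conflict with 9.1.

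A reader might further infer that the 2- and 4-dose arms have no plasma steady state. That does not follow: a repeating weekly regimen reaches a periodic steady state.

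Finally, section 13 does not itself mention the pregnancy contrast. That contrast is where plasma exposure is compared between groups, but it is secondary, and 7.3.2 calls secondary analyses hypothesis generating.

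**Conclusion.** The point holds in a limited form. The comparison stated in 7.3.2(2) does not support a claim about how much plasma exposure differs, because time since dose is neither fixed by design nor in the model, and the reason for ignoring it covers TFV-DP only.

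The likely cost is precision: a variance multiplier of about 1.7 to 3.6 for one draw per woman, or about 1.1 to 1.5 over five independently timed visits. Bias is a possibility that the documents do not establish; a gap of 4 to 8 h would produce 11% to 37%. A reader might infer that timing could account for the whole 30% to 58% pregnancy effect. The figures do not support that: only the 30% end is within reach of such gaps, and only towards the 12 h half-life. A 45% to 58% artefact would need roughly 10 to 30 h, and 30 h exceeds a dosing interval.

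All plasma sizes rest on the assumed 12 to 24 h half-life; the precision figures also rest on the borrowed CV. A steeper decline soon after the peak would shorten the gaps needed. The primary TFV-DP analyses are unaffected. This is a cheap improvement to a secondary analysis.

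**What to change.** 1. Record the clock time of the last observed dose and of each pharmacology draw. This has to be in place before visits take place, since missing times may not be recoverable.
2. In 7.3.2(2), state that plasma TFV and FTC are compared between the pregnant women and the non-pregnant 7-dose arm, with time since last dose in the model. Alternatively, name the population PK model of section 13, with pregnancy as a covariate, as that analysis.
3. If neither is done, limit the section 13 statement on the size of the difference to a descriptive one.
4. Reconcile 4.8 with 9.1 on whether pharmacology samples at the monthly visits are taken before the dose.

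The cost is two recorded times per visit, one model term and some wording.
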